2 STUDY DESCRIPTION

2.1 Study Design

This is a 12 week randomized, double-blind, placebo-controlled, dose-ranging study with adaptive design features based on an interim analysis. The study will initially have a Screening Period (with 2 screening visits for subjects that require DMARD washout) and be followed by up to 12 weeks of DB treatment and a 30 day follow-up period.

Four treatments will be administered: placebo, 100, 200, and 350 mg of BMS-986142 daily for 12 weeks. Based on the Week 4 interim analysis, one or more BMS-986142 doses and/or sample size may be subsequently modified.

Screening Period:

[figure not shown]
The standard duration of the Screening Period is up to 30 days, with two Screening Visits allowed for subjects who require washout of hydroxychloroquine/chloroquine and/or sulfasalazine. Subjects who are on hydroxychloroquine/chloroquine and/or sulfasalazine in combination with MTX will have hydroxychloroquine/chloroquine and/or sulfasalazine discontinued at the beginning of the Screening Period as they need to be off those medications for at least 30 days and need to be rescreened prior to randomization (Day 1). Should more time be needed, the duration of the Screening Period may be extended up to another week (total of five weeks) depending on current DMARDs washout, drug stabilization, MRI technical issues, and subject scheduling.

Subjects with moderate to severely active RA who have had an inadequate response to MTX or up to 2 TNF inhibitors will receive BMS-986142 or placebo daily for up to 12 weeks, followed by a 30 day follow-up period.

Double-Blind Period:

Upon meeting the inclusion criteria and none of the exclusion criteria and completing the screening period, approximately 328 subjects will be randomized to 1 of the 4 treatment arms in an equal ratio as shown in the study schematic below.

Figure 1: Study Design Schematic

During this period, the dose of methotrexate, NSAIDs, and oral prednisone (or its equivalent) should remain stable. Intra-articular corticosteroid injections and intra-muscular injections are not permitted. Analgesics are permitted with certain restrictions (see [Section 3.2](#)).

At the end of the DB period, alternate therapies for RA should be discussed with subjects.

Interim Analyses:

Interim Analyses (IA) of clinical and PK data will be performed after approximately 20 subjects per treatment arm reach Week 4 (complete 4 weeks of treatment or discontinue) and complete the specified assessments for efficacy (e.g., DAS28-CRP), safety, and PK. Details of interim analyses are described in [Section 7.9](#) (Interim analysis).

2.2 Treatment Assignment

After completion of all screening evaluations, on Day 1, all eligible subjects will be randomly assigned to 1 of 4 treatment arms (BMS-986142, 100 mg; BMS-986142, 200 mg; BMS-986142, 350 mg; and Placebo) in an equal ratio. To randomize a subject, a phone call will be placed into the randomization option of the interactive voice response system (IVRS) in order to obtain a subject's randomized treatment assignment. Randomization will be assigned in the order in which subjects qualify for treatment, not in the order of study enrollment. The IVRS will be available 24-hours a day, 7 days a week, via a toll-free number. Randomization will be stratified by prior treatment status (MTX-IR vs TNF-IR) and geographic region.

Specific instructions (including an enrollment/randomization worksheet) for the central enrollment and randomization procedure using an IVRS will be provided to the site.

Randomized schedules will be generated and kept by the Randomization Group within Drug Supply Management of Bristol-Myers Squibb. The randomization ratio may be adjusted if any dose arm will be discontinued and/or new dose arm will be added based on Week 4 interim analysis.

2.3 Blinding and Unblinding

Blinding of treatment assignment is critical to the integrity of this clinical study. However, in the event of a medical emergency or pregnancy in an individual subject in which knowledge of the investigational product is critical to the subject's management, the blind for that subject may be broken by the investigator. The subject's safety takes priority over any other considerations in determining if a treatment assignment should be unblinded.

Before breaking the blind of an individual subject's treatment, the investigator should determine that the unblinded information is necessary, ie, that it will alter the subject's immediate management. In many cases, particularly when the emergency is clearly not related to the investigational product, the problem may be properly managed by assuming that the subject is receiving active product. It is highly desirable that the decision to unblind treatment assignment be discussed with the Medical Monitor, but the investigator always has ultimate authority for the decision to unblind. The Principal Investigator should only call in for emergency unblinding AFTER the decision to discontinue the subject has been made.

For this study, the method of unblinding for emergency purposes is through the IVRS.

For information on how to unblind in case of an emergency, consult the IVRS manual

In cases of accidental unblinding, contact the Medical Monitor and ensure every attempt is made to preserve the blind.

Any request to unblind a subject for non-emergency purposes should be discussed with the Medical Monitor.

The Bioanalytical Sciences department or its designate will be unblinded to the randomized treatment assignments in order to minimize unnecessary analysis of samples from control group subjects.

To implement the adaptive design that is planned in advance, an interim analysis will be conducted prior to the formal locking of the study database. In order to allow for a high quality and/or validated data analysis and a timely analysis of data, the unblinded team may consist of up to two people from each relevant function role within BMS.

- Global Biometric Sciences - Up to 2 statisticians and 2 programmers
- Clinical Pharmacology and Pharmacometrics - Up to 2 pharmacometric and pharmacokinetic scientists and 2 pharmacometric programmers
- Clinical Biomarkers - Up to 2 clinical biomarker scientists

- Bioinformatics -Up to 2 bioinformaticians

This configuration ensures that the unblinded team has the resources to independently conduct its own analyses. The study team does not have access to any unblinded data and is not involved in the review or discussion of unblinded data.

2.4 Protocol Amendments

Not applicable.

3 OBJECTIVES

3.1 Primary Objective

To compare the efficacy of BMS-986142 versus placebo (PBO) on a background of MTX as assessed by ACR20 and ACR70 response rates at Week 12.

3.2 Secondary Objectives

- Assess additional efficacy outcomes of BMS-986142 at Week 12 and over 12 weeks of treatment as measured by ACR20, ACR50 and ACR70 response rates, DAS28-CRP change from baseline, DAS28-ESR change from baseline, Clinical Disease Activity Index (CDAI), Simplified Disease Index (SDAI), and Boolean remission.
- Assess the safety and tolerability of BMS-986142.
- Evaluate Ctrough of BMS-986142.
- Assess the efficacy of BMS-986142 + MTX to MTX alone in reducing synovitis, osteitis, bone erosion and cartilage loss in hands/wrists by MRI at Weeks 4, and 12, from baseline.

4 ENDPOINTS

4.1 Primary Efficacy Endpoint(s)

Co-Primary endpoints:

- Proportion of subjects who achieve ACR20 response rate at Week 12
- Proportion of subjects who achieve ACR70 response rate at Week 12

4.2 Secondary Efficacy Endpoint(s)

- Proportion of subjects who achieve ACR20 over time from baseline to Week 12
- Proportion of subjects who achieve ACR50 over time from baseline to Week 12
- Proportion of subjects who achieve ACR70 over time from baseline to Week 12
- Proportion of subjects who achieve DAS28-CRP < 2.6 over time from baseline to Week 12
- Proportion of subjects who achieve DAS28-ESR < 2.6 over time from baseline to Week 12
- Proportion of subjects who achieve CDAI \leq 2.8 over time from baseline to Week 12
- Proportion of subjects who achieve SDAI \leq 3.3 over time from baseline to Week 12
- Proportion of subjects who achieve Boolean Remission over time from baseline to Week 12
- Change from baseline in DAS28-CRP score over time up to Week 12
- Change from baseline in DAS28-ESR score over time up to Week 12
- Change from baseline in CDAI score over time up to Week 12
- Change from baseline in SDAI score over time up to Week 12
- Change from baseline in RAMRIS scores of synovitis, osteitis (bone marrow edema), bone erosion and cartilage loss (joint-space narrowing) (MRI) to Week 4, and Week 12

[figure not shown]
4.3 Safety Endpoints

- Incidence and severity of all Adverse Events (AEs), Serious AEs (SAE), and Events of Special Interest (EOSI)
- Incidence and severity of clinically significant changes in vital signs
- Incidence and severity of clinically significant electrocardiogram (ECG) abnormalities
- Incidence and severity of clinically significant abnormalities in general laboratory tests

4.4 Pharmacokinetic Endpoints

Through: Trough level plasma concentration of BMS-986142 at time points specified in Section 5.5 of the protocol.

5 SAMPLE SIZE AND POWER

The sample size calculation is driven by the power to compare the proportion of subjects who achieve ACR70 response at Week 12 between each BMS-986142 dose arm and placebo arm without multiplicity adjustment. The target population consists of mixed subjects who are TNF-IR ($\geq 80\%$) and MTX-IR ($\leq 20\%$). For co-primary endpoint of ACR70 at Week 12, 82 subjects per arm will provide $\sim 80\%$ power to detect a treatment difference of 14% at the type I error rate of $\alpha = 0.05$ (two-sided), assuming the placebo response rate of 2.5%. The assumed treatment difference of 14% is double of 7% that was median difference observed from historical data on approved drugs across different mechanism of actions (MOAs).

If the placebo response rate in ACR70 at Week 12 is higher than planned 2.5% (eg, 5%), 82 subjects per arm can still provide $> 70\%$ power to detect a difference of 14%.

For the population of TNF-IR ($\geq 80\%$), 65 subjects per arm will provide 68% power to detect a treatment difference of 14% in ACR70 at the Type 1 error rate of $\alpha = 0.05$ (two-sided), assuming the placebo response rate is 2.5%.

For the other co-primary endpoint of ACR20 at Week 12, 82 subjects per arm will provide 98% power to detect a difference of 31% over placebo at the type I error rate of $\alpha = 0.05$ (two-sided), assuming placebo response rate of 22%. The assumed treatment difference of 31% and placebo response rate of 22% were based on the observed data from approved drugs across different MOAs.

For the population of TNF-IR ($\geq 80\%$), 65 subjects per arm will provide 94% power to detect a treatment difference of 30% in ACR20 at the Type 1 error rate of $\alpha = 0.05$ (two-sided), assuming the placebo response rate is 18%.

An interim analysis (IA) will be conducted when about 20 subjects reach week 4 (complete 4 weeks of treatment or discontinue). Based on the totality of efficacy, safety, and PK at Week 4 IA, the following adaptation(s) may be recommended:

- Stop ineffectual or unsafe dose(s)
- Introduce new dose(s) arms if needed and enroll (up to about 82 subjects per arm)
- Complete full enrollment for all effective arms (up to about 82 subjects per arm)

- Stop the study enrollment if all dose arms are stopped for safety or futility;

The total sample size varies depending on the interim analysis results (range from 328 to 408 subjects). The details of interim analysis and the criteria to adapt dose arm(s) and stop for futility are specified in the [section 7.9](#).

6 STUDY PERIODS, TREATMENT REGIMENS AND POPULATIONS FOR ANALYSES

6.1 Study Periods

The following periods are defined in this SAP for the purpose of analyses and reporting.

Pre-treatment period: It covers the time period which starts from the day of enrollment and lasts until the initiation of randomized double-blind treatment

Double-blind (DB) period: It starts at the time of the first dose of blinded treatment (BMS-986142 or placebo) and lasts until the date of the last dose of double-blinded treatment + 30 days or the start of first dose in long-term extension period.

6.2 Treatment Regimens

The eligible subjects will be randomized to receive BMS-986142 (100mg, 200mg and 350mg) or Placebo daily (double-dummy) at equal ratio. There may be an instance of new treatment group(s) added and one or more treatment arms (other than Placebo) may be dropped based on interim analysis. For more details, see study design in the Protocol.

6.3 Populations for Analyses

- All Enrolled Subjects: All subjects who sign an informed consent.
- All Randomized Subjects: All subjects who are randomized to a treatment.
- Modified Intent-to-Treat (MITT) Analysis Population: All randomized subject who have received at least one dose of the study medication. Subjects will be grouped according to the treatment to which they were randomized by IVRS at the start of the study. The MITT analysis population will also be referred to as “All Randomized and Treated Subjects”.
- As-Treated Analysis Population: All Subjects who have received at least one dose of study medication. Subjects will be grouped according to the treatment that they actually received as opposed to the treatment to which they were randomized. Subjects will be grouped on an as randomized basis unless the subject received the incorrect medication for the entire period of treatment. In that case, the subject will be analyzed in the treatment group associated with the incorrect medication he/she received.
- Efficacy Analysis Population: This is a subset of the MITT Analysis Population where the subjects who are randomized to a treatment arm and discontinued based on the interim analysis are excluded. All efficacy results involve statistical comparison or modeling will be based on this analysis population unless otherwise specified.
- [REDACTED]
- [REDACTED]
- Pharmacokinetic Population: All subjects who have received BMS-986142 and have any available concentration-time data.

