8.2 Populations for Analyses

- All Enrolled Subjects, defined as all subjects who sign an informed consent;
- All Randomized Subjects, defined as all subjects who are randomized to a treatment;
- All Randomized and Treated Subjects, defined as modified intent-to-treat (mITT) subjects who are randomized and receive at least one dose of study medication;
- All Treated Subjects, defined as all subjects who receive at least one dose of study treatment;
- 
- Pharmacokinetic Population, defined as all subjects who receive any study medication and have any available concentration-time data.

All subjects who receive at least one dose of study treatment (all treated subjects) will be included in the safety analysis population and mITT subjects will be included in the efficacy analysis population. More details will be provided in the statistical analysis plan.

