8.4.2 Efficacy Analyses

Primary efficacy analysis:

The Chi-square tests will be used to compare the ACR70 response rates at Week 12 between each of the active treatment arms and the placebo arm. The p-value will be provided for each comparison between the active treatment and the placebo arm. In addition, the difference of the response rates between each active treatment and the placebo will be estimated and their corresponding 95% confidence interval will be calculated.

All subjects discontinuing prematurely during the double-blind period, regardless of reason, will be counted as non-responders at subsequent visits. Summaries will be performed using mITT analysis population. The same analysis will be performed for ACR20 response at Week 12.

Secondary efficacy analysis:

- Proportion of subjects who achieve ACR20 over time from baseline to Week 12
- Proportion of subjects who achieve ACR50 over time from baseline to Week 12
- Proportion of subjects who achieve ACR70 over time from baseline to Week 12
- Proportion of subjects who achieve DAS28-CRP < 2.6 over time from baseline to Week 12
- Proportion of subjects who achieve DAS28-ESR < 2.6 over time from baseline to Week 12
- Proportion of subjects who achieve CDAI \leq 2.8 over time from baseline to Week 12
- Proportion of subjects who achieve SDAI \leq 3.3 over time from baseline to Week 12
- Proportion of subjects who achieve Boolean Remission over time from baseline to Week 12

For each of the above endpoints, the estimate and its corresponding 95% confidence interval will be calculated for the difference of the proportions between each active treatment arm and the placebo arm at the specified visit, similar to the primary analysis.

For each of the following endpoints, the mixed effect model will be fit with treatment and visit as the fixed effects and measurements within each subject as the repeated measurements. The baseline value will be added into the model as a covariate if necessary. Based on the mixed effect model, the estimate and 95% confidence interval will be calculated for the difference between each active treatment and the placebo at each specified visit:

- Change from baseline in DAS28-CRP score over time up to Week 12
- Change from baseline in DAS28-ESR score over time up to Week 12
- Change from baseline in CDAI score over time up to Week 12
- Change from baseline in SDAI score over time up to Week 12

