- Change from baseline in RAMRIS Scores of synovitis, osteitis, bone erosion and cartilage loss to Week 4 and Week 12

The details of the analyses, endpoints and grouping schemes (treatment groups) will be provided in the statistical analysis plan (SAP).

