If the predictive probability of $\Delta\Delta$ DAS28 improvement being greater than 1.0 is high (eg, > 80%) in all active arm(s), the BMS team may recommend to maintain the study design and treatment arms. In this scenario, all enrolled subjects will continue the treatments without modifications and also be included in the final analysis for the existing dose arm. The BMS team may also recommend adding an additional dose arm at lower dose level than current active doses to explore the suboptimal dose. In this case, approximately 40 subjects will be randomized into the suboptimal dose arm along with existing efficacious dose arms. The new suboptimal dose level may be selected based on dose/exposure response analysis.

If the predictive probability of $\Delta\Delta$ DAS28 improvement being greater than 1.0 is high (eg, >80%) in 2 BMS-986142 arms (mid and high dose arms), then the BMS team may recommend to maintain the study design and these 2 treatment arms. The enrolled subjects will be carried over in the existing dose arm and also be included in the final analysis for the existing dose arm. The subjects enrolled in the low dose arm will continue the treatment if they have received at least 1 treatment and treatment is considered safe before the interim analysis is completed. The decision to continue enrolling subjects into this treatment arm will depend on the collective assessment of the efficacy endpoints (beyond DAS28) and safety data. Even if the relationship between dose/exposure and response is adequately characterized from the interim analysis, a lower, sub-optimal dose (approximately 40 subjects) may be added if further subgroup analysis and collective data suggest a distinct trend in each subgroup.

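### The SAP runs the co-primary tests on an interim-dependent subset of mITT that the protocol does not provide for, without saying whether it removes subjects or whole arms

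*SAP*

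**What the plan says.** **Protocol.** Section 8.2 defines mITT as subjects randomized and given at least one dose, and states that "mITT subjects will be included in the efficacy analysis population". Its next sentence leaves further detail to the SAP. Section 8.4.2 repeats the choice for the primary analysis: "Summaries will be performed using mITT analysis population". It also fixes the handling of dropouts: "All subjects discontinuing prematurely during the double-blind period, regardless of reason, will be counted as non-responders at subsequent visits". It asks for a p-value for each active arm against placebo, and leaves details of analyses, endpoints and treatment grouping to the SAP.

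**SAP.** Section 6.3 defines MITT in the same way, then adds an Efficacy Analysis Population: the MITT set from which "subjects who are randomized to a treatment arm and discontinued based on the interim analysis are excluded". This is the default for every comparative or modelled efficacy result. Sections 7.5 and 7.5.1 use it for the co-primary chi-square tests, and 7.5.3 to 7.5.5 use it or subsets of it. Section 8.5.1 imputes non-response after premature discontinuation.

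**Closed arms.** Under SAP 7.9, dosed subjects in an arm projected to be ineffective continue to the end of the double-blind period, while an unsafe arm stops at once. Protocol 8.5 makes the same distinction. For retained arms, both documents say that enrolled subjects will "also be included in the final analysis for the existing dose arm". Neither says this, or its opposite, for closed arms.

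**Dates.** The SAP is version 1.0 (12/04/2015). The protocol is Revised Protocol 03 (29-Oct-2017).

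**The concern.** The two documents name different populations for the same primary analysis, and membership of the SAP's population depends on unblinded interim results. The clause does not make clear what is discontinued, and the consequence differs:

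- **Subject.** The clause acts mainly on an arm stopped immediately for safety. Its subjects still on drug are deleted, where Protocol 8.4.2 and SAP 8.5.1 would count them as non-responders.
- **Arm.** Week 12 data from a closed dose are collected but left out of the comparison with placebo. What remains for that dose is the interim Bayesian and descriptive summaries, the exposure-response work, and the disposition and safety tables.

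In a dose-ranging trial, the Week 12 response on a closed dose is part of the dose-response evidence.

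**Working it through.** **1. Which reading does the text support?**

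- *Arm.* SAP 2.2 lets the randomization ratio change "if any dose arm will be discontinued and/or new dose arm will be added based on Week 4 interim analysis", so the SAP itself uses the word of an arm. SAP 6.2 adds that "one or more treatment arms (other than Placebo) may be dropped based on interim analysis".
- *Subject.* In SAP 6.3 the grammatical subject of the clause is the subjects. Under SAP 7.9, dosed subjects in an ineffective arm are not discontinued. The note in SAP 7.5 says that after an all-arm enrollment stop the sensitivity, per-protocol, subgroup and additional analyses may be skipped. It does not list the primary analysis, which implies that this still runs.

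The text does not settle the question, so both readings are followed.

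**2. The plan's own figure.** Protocol 8.1 states about 90% power for ACR70 (82 per arm, 2.5% v 19.5%, two-sided 0.05). With a continuity correction:

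- difference less correction: 0.17 − 0.5 × (2/82) = 0.1578
- null SE: √(0.11 × 0.89 × 2/82) = 0.0489
- alternative SE: √((0.025 × 0.975 + 0.195 × 0.805)/82) = 0.0470
- power: Φ((0.1578 − 1.96 × 0.0489)/0.0470) = Φ(1.32) = 90.6%

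The figure reproduces, and this point does not change it.

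**3. Subject reading.** Let a safety-stopped arm have n treated subjects, k of them taken off drug because of the interim, and r Week 12 responders. Under the protocol the rate is r/n. Under the exclusion it is r/(n − k), larger by the factor n/(n − k) whenever r > 0. The documents do not give k. For illustration, at n = 20 and assumed k of 2, 5 or 10, the factor is 20/18 = 1.11, 20/15 = 1.33 or 20/10 = 2.00. Subjects who had already completed Week 12 stay in.

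**4. Arm reading.** The interim takes place at about 20 subjects per arm, so at least about 20 treated subjects per closed arm leave: 20/82 = 24% of a full arm. The number dosed by the time of closure is not given.

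**5. What mITT keeps for one closed arm of 20.** Rates are from Protocol 8.1: ACR20 placebo 33%, active between 33% and 67%. The 95% half-width is 1.96 × √(0.33 × 0.67/n₀ + p(1 − p)/20), where n₀ is the number on placebo.

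| Placebo n₀ | p = 0.33 or 0.67 | p = 0.50 |
|---|---|---|
| 82 | 0.230 | 0.242 |
| 20 | 0.291 | 0.301 |

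Power at 20 v 82 for ACR20 (33% v 67%): pooled rate (82 × 0.33 + 20 × 0.67)/102 = 0.397; null SE 0.1220; alternative SE 0.1173.

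- Uncorrected: Φ((0.34 − 1.96 × 0.1220)/0.1173) = 80.5%.
- With the correction of step 2, the difference becomes 0.34 − 0.5 × (1/82 + 1/20) = 0.3089 and power is Φ(0.595) = 72%.

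For ACR70 (2.5% v 19.5%) at 20 v 82, power is 73.0% by the uncorrected formula and 65.4% by Fisher's exact test.

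At an ACR70 rate of 2.5%, 20 × 0.025 = 0.5 responders are expected in 20 subjects, so the exact interval of SAP 7.1 applies. For 0/20 its upper limit is 1 − 0.025^(1/20) = 16.8%.

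**The case against.** **The protocol defers to the SAP.** Protocol 8.2 promises more detail there, and 8.4.2 leaves treatment grouping to it. This softens the conflict but does not remove it. Detail can elaborate a named population; removing treated subjects because of an interim result changes it.

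**The subject reading is benign for futility.** This stands. A reader might infer that any dose arm closed at the interim loses its Week 12 comparison. The documents do not support that as a general statement. It requires the arm reading, while the grammar of SAP 6.3, the continuation rule in SAP 7.9 and the note in SAP 7.5 all point to the subject.

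**The worst case needs two assumptions.** A reader might go further: all three active arms close, 60 of 80 interim subjects (75%) leave, and no test can be run. That needs the arm reading and also an all-arm enrollment stop treated as discontinuation of the arms. SAP 7.9 describes such a stop as ending enrollment while treated subjects continue, and the SAP 7.5 note presupposes an analysis.

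**Redaction.** Two populations in SAP 6.3 are hidden, as are blocks after SAP 7.7 and at the end of 7.9. The absence of another analysis for closed arms can be stated only for the visible text.

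**Limited reach.** On the arm reading, tests of retained arms are unaffected, because placebo cannot be dropped. The protocol synopsis reports a sponsor decision to stop recruitment on 30 November 2017, but does not attribute it to the interim analysis.

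**Conclusion.** The conflict is real on either reading. SAP 6.3, 7.5 and 7.5.1 depart from the mITT analysis of Protocol 8.2 and 8.4.2 through an exclusion that the protocol does not provide for, and the key word is undefined.

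- **If it means the subject:** futility-closed arms are intact. In a safety-stopped arm, the apparent response rate rises by n/(n − k). The size is unknown because k is not given.
- **If it means the arm:** a closed dose with at least about 20 treated subjects has no final Week 12 comparison in the visible text.

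The second result rests on the interim size of about 20 per arm and on the visible text alone. Nothing in the documents shows that the clause took effect. This should be corrected, but it does not undermine the tests of retained doses.

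**What to change.** In SAP 6.3, 7.5 and 7.5.1, make mITT, grouped as randomized, the primary efficacy population, as in Protocol 8.2 and 8.4.2. Apply the existing non-responder rule of SAP 8.5.1 to anyone taken off drug after the interim, so that all dosed subjects of closed arms stay in the final analysis. If the reduced set is kept, make it supportive only and define *discontinued* as subject or arm.

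While the two documents are being aligned, note that they also differ on enrollment into weaker arms. SAP 7.9 says that no new subjects will enter, whereas Protocol 8.5 leaves this to a collective assessment of efficacy and safety. The number of subjects in a closed arm depends on this, so the two sections must be reconciled.

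**Cost.** Wording only, with no new data. A small closed arm will be reported with a wide interval: an ACR20 half-width of about 23 to 24 points at 20 against 82 placebo subjects, and 29 to 30 at 20 against 20. Because recruitment stopped before the planned number, the placebo arm may be smaller than 82.

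Two further choices are optional and not part of the correction: comparing a closed arm only with concurrently randomized placebo subjects, and omitting its p-value. Both would depart from Protocol 8.4.2 and would need to be stated there.
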